6.1.4. AECOPD visits and daily questionnaires

The time until first AECOPD as of 1 month post-Dose 2 will be computed with exact 95% CI by group. Subjects who exacerbate before 1 month post-Dose 2 will not be taken into account in this analysis.

The number of morning e-dairy (PHT) alerts (resp. evening e-diary alerts (EXACT-PRO)) with and without corresponding site visits will be tabulated. The reason for inconsistency between morning e-diaries and site visits will also be presented.

The number of exacerbation site visits with confirmed AECOPD with and without morning e-diary alerts (resp. evening e-diary alerts (EXACT-PRO)) will be tabulated along with the reason for no e-diary alert.

Concordance/discordance of exacerbations periods as defined clinically or via the morning diary cards or the evening diary cards will be tabulated and presented graphically.

The percentage of spontaneous exacerbation visits will be tabulated as well as the percentage of monthly visits with recovered/stable status.

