The lungs are known to be colonised with different strains of bacteria [[Erb-Downward](#), 2011]. In COPD patients, acquisition of new bacterial strains is believed to be an important cause of AECOPD [[Sethi](#), 2002]. Although estimates vary widely, Non-typeable *Haemophilus influenzae* (NTHi) appears to be the main bacterial pathogen associated with AECOPD (11-38%), followed by *Moraxella catarrhalis* (*M. catarrhalis*) (3-25%) and *Streptococcus pneumoniae* (*S. pneumoniae*) (4-9%) [[Alamoudi](#), 2007; [Bandi](#), 2003; [Hutchinson](#), 2007; [Ko](#), 2007; [Larsen](#), 2009; [Murphy](#), 2005; [Papi](#), 2006; [Sethi](#), 2002; [Sethi](#), 2008].

Reducing the frequency and severity of AECOPD is one of the main goals of COPD maintenance treatment. The severity of AECOPD can be graded according to the intensity of medical intervention required (see [Table 2](#)) [[Wedzicha, 2007](#)].

Table 2 Classification of severity of AECOPD

Grade	Intensity of medical intervention
Mild	Can be controlled with an increase in dosage of regular medications
Moderate	Requires treatment with systemic corticosteroids and/ or antibiotics
Severe	Requires hospitalisation

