5.2. Inclusion criteria for enrolment

Deviations from inclusion criteria are not allowed because they can potentially jeopardise the scientific integrity of the study, regulatory acceptability or subject safety. Therefore, adherence to the criteria as specified in the protocol is essential.

All subjects must satisfy ALL the following criteria at study entry:

- Subjects who, in the opinion of the investigator, can and will comply with the requirements of the protocol (*e.g.* electronic Diary Card completion, number of blood draws, sputum sampling, pre- and post-bronchodilator spirometry, return for follow-up visits).
- A male or female between, and including, 40 and 80 years of age at the time of the first vaccination.
- Written informed consent obtained from the subject.

- Confirmed diagnosis of COPD (based on post-bronchodilator spirometry) with forced expiratory volume in 1 second (FEV₁) over forced vital capacity (FVC) ratio (FEV₁/FVC) < 0.7, **AND** FEV₁ < 80% and ≥ 30% predicted (GOLD 2 and 3).

- Current or former smoker with a cigarette smoking history of ≥ 10 pack-years.
Refer to the [glossary of terms](#) for the definitions of pack-years and of current and former smoker.

- Stable COPD patient* with documented history (e.g. medical record verification) of at least 1 moderate or severe AECOPD within the 12 months before Screening.

* Patient for whom the last episode of AECOPD is resolved for at least 30 days at the time of Screening.

Refer to the Study Procedures Manual (SPM) for details on what is accepted as documented history of AECOPD. Refer to [Table 2](#) for the definitions of moderate and severe AECOPD.

- Regular sputum producer.
- Capable to comply with the daily electronic Diary Card completion throughout the study period, according to investigator's judgement at Visit 1.

Refer to the SPM for recommendations on what is considered adequate compliance by Visit 1.

- Female subjects of non-childbearing potential may be enrolled in the study.
 - Non-childbearing potential is defined as current tubal ligation, hysterectomy, ovariectomy or post-menopause.
Refer to the [glossary of terms](#) for the definition of menopause.
- Female subjects of childbearing potential may be enrolled in the study, if the subject:
 - has practiced adequate contraception for 30 days prior to vaccination, and
 - has a negative pregnancy test on the day of vaccination, and

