6.5.2. List of study procedures during AECOPD-driven study visits and phone contacts

In addition to the scheduled study visits, *ad-hoc* AECOPD-driven study contacts will take place for each AECOPD occurring from first vaccination up to study conclusion. The procedures to be performed during these contacts are listed in [Table 8](#).

In case of AECOPD occurring before Visit 1, subjects should be treated outside the study according to standard practice. These subjects can only continue in the study if the entire Screening Visit is repeated after they are stable for at least 30 days.

Table 8 List of study procedures during AECOPD-driven study visits and phone contacts

Type of contact	AECOPD visit	End of AECOPD contact(s) (phone call[s] and/ or visit[s])
Timepoint	within 96 hours of onset symptoms	at least every 2 weeks as of AECOPD visit until AECOPD has resolved ^(a)
Sampling timepoint	AECOPD	
Record date of visit	●	
Physical examination	○	○ ^(b)
Chest X-ray ^(c)	●	
Confirm AECOPD and record its start date	●	
Blood sampling:		
For biomarkers (~12.8 mL)	●	
For haematology assessment (~2 mL)	●	
Sputum sampling ^(d)	●	
HRQOL questionnaires:		
CAT	x	
mMRC	x	
Record healthcare use for AECOPD (medical record review)	○	●
Record AEs	●	●
Report SAEs	●	●
Report pregnancies ^(e)	●	●
Record concomitant medications/products and vaccinations	●	● ^(b)
Record intercurrent medical conditions requiring medical attention	●	●
Record AECOPD severity	○	●
Record AECOPD end date		●

● is used to indicate a study procedure that requires documentation in the individual eCRF.

○ is used to indicate a study procedure that does not require documentation in the individual eCRF.

x is used to indicate a study procedure that does not require documentation in the individual eCRF as the data will be directly transferred from the provider to GSK.

^a End of AECOPD phone calls/ visits should be scheduled at least every 2 weeks, until the AECOPD has resolved.

Only the contact during which the end date of the AECOPD can be determined will be recorded in the eCRF as the end of the AECOPD contact. All intermediate contacts should be recorded on source documentation.

^b Only applicable if the contact is a visit (not for phone calls).

^c Only if clinically indicated to exclude another cause of worsening of symptoms (e.g. pneumonia).

^d Only if, in the opinion of the investigator, it is safe for the subject.

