6.1.3. Analysis of impact of the investigational vaccine on AECOPD incidence

The analysis will be performed on the ATP cohort for efficacy. If the percentage of vaccinated subjects excluded from the ATP cohort for efficacy is more than 10%, a second analysis based on the TVC will be performed to complement the first analysis.

The following incidence rates will be computed over a period starting 1 month post-Dose 2 and lasting for 1 year, with 95%CI:

- NTHi-associated moderate and severe AECOPD. (See definition in section 7.1.4)
- NTHi-associated all-severity AECOPD.
- All-cause moderate and severe AECOPD.
- All-cause, all-severity AECOPD.

Vaccine efficacy (VE) for AECOPD events will be defined as:

$$VE (AECOPD) = 1 - R_{vaccine} / R_{control}$$

with:

- $R_{vaccine}$ = average yearly incidence rate of AECOPD events per subject in the group 10-AS01E.
- $R_{control}$ = average yearly incidence rate of AECOPD events per subject in the Control group.

In case the 95% CI of the VE cannot be estimated, *e.g.* when no event is observed in the group 10-AS01E (leading to a VE of 100%), then an exact procedure will be used to estimate a VE and its 95% CI. This exact procedure will be based on the number of subjects with event instead of on the average number of event per subject in each group.

Statistical Analysis Plan

Study alias & e-track number(s): NTHi-004 (200157)

VE in the prevention of NTHi-associated moderate and severe AECOPD and its 95% CI will be calculated.

VE in the prevention of NTHi-associated all-severity AECOPD, of all-cause moderate and severe AECOPD and of all-cause, all-severity AECOPD and their 95% CI will also be calculated.

The 95%CI of the incidence rate will be computed using a model which accounts for repeated events. The Generalised linear model assuming the Negative Binomial distribution for the response variable with logarithm as link function, and the logarithm of time for follow-up as an offset variable will be used. In addition, the following covariates (as per randomization) will be taken into account:

- country,
- number of moderate/severe exacerbations reported in the 12 months prior to enrolment,
- COPD status at enrolment (derived by GSK from the Visit 1 spirometry results)
- Age (below or equal to median/above median)

If the model does not converge, the Poisson distribution will be used instead of the Negative Binomial one.

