The frequency of all these AECOPDs will be presented. The estimated incidence rate with 95%CI of AECOPDs in which Hi (resp. Mcat, Sp) is present in culture and was not present in the previous visit estimated by a Generalised linear model assuming the Negative Binomial distribution will be estimated.

Time to first AECOPD event by baseline status - Cox regression model

The Cox's regression model including the risk factors:

- country,
- number of moderate/severe exacerbations reported in the 12 months prior to enrolment,
- COPD status at enrolment (derived by GSK from the Visit 1 spirometry results)
- Age (below or equal to median/above median)

as covariates (as per randomization) will be performed to model the time until the first occurrence of AECOPD episodes. Additional stratification/risk factor may be defined during the analyses like sex factor as exploratory analysis.

Statistical Analysis Plan

Study alias & e-track number(s): NTHi-004 (200157)

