7.1.3. Immunogenicity

- For a given subject and the analysis of a given immunogenicity measurement, missing or un-evaluable measurements will not be replaced.
- A seronegative subject is defined as a subject whose antibody concentration is below the assay cut-off value.
- A seropositive subject is defined as a subject whose antibody concentration is greater than or equal to the assay cut-off value.
- Antibody concentrations below the assay cut-off will be given an arbitrary value of half the assay cut-off for the purpose of geometric mean concentration (GMC) calculation.
- Calculation of the GMCs will be performed by taking the anti-logarithm in base 10 (anti-log10) of the mean of the log10 concentration transformations.

Statistical Analysis Plan

Study alias & e-track number(s): NTHi-004 (200157)

- The assay cut-off is the value under which there is no quantifiable result for which no accuracy and precision can be reported. For an assay with a specific 'cut_off' , numerical immuno result is derived from a character field (rawres):
 - If rawres is 'NEG' or '-' or '(-)', numeric result= cutt_off/2,
 - if rawres is 'POS' or '+' or '(+)', numeric result = cut_off,
 - if rawres is '< value' and value<=cut_off, numeric result =cut_off/2,
 - if rawres is '< value' and value>cut_off, numeric result =value,
 - if rawres is '> value' and value<cut_off, numeric result =cut_off/2,
 - if rawres is '> value' and value>=cut_off, numeric result =value,
 - if rawres is '<= value' or '>= value' and value<cut_off, numeric result =cut_off/2,
 - if rawres is '<= value' or '>= value' and value>=cut_off, numeric result =value,
 - if rawres is a value < cut_off, numeric result = cut_off/2,
 - if rawres is a value >= cut_off, numeric result = rawres,
 - else numeric result is left blank.
- All CI computed will be two-sided 95% CI.

Impact of the investigational vaccine on AECOPD

- For a given subject and the analysis of a given laboratory assay, missing or un-evaluatable measurements will not be replaced.
- Subjects who did not have any sputum collected during at least 1 AECOPD (if at least 1 AECOPD occurred) will not be taken into account for the NTHI-associated AECOPD analyses.

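### The by-group time to first AECOPD starts at 1 month post-Dose 2 but leaves out everyone who exacerbated since Dose 1, so it describes a selected subset and not the population of the incidence analysis that starts on the same date

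*SAP*

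**What the plan says.** SAP Amendment 1, section 6.1.4, states: "The time until first AECOPD as of 1 month post-Dose 2 will be computed with exact 95% CI by group". The next sentence is the exclusion: "Subjects who exacerbate before 1 month post-Dose 2 will not be taken into account in this analysis". Protocol 11.10 has the same two sentences, and so does SAP version 1.

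Four other places bear on it:

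- **Endpoint.** Protocol 11.3 and SAP 4.3 define time to first AECOPD in all subjects.
- **Incidence and vaccine efficacy.** SAP 6.1.3: "The following incidence rates will be computed over a period starting 1 month post-Dose 2 and lasting for 1 year". It has no exclusion for an earlier AECOPD, and neither do the criteria for the ATP efficacy cohort (SAP 5.4, Protocol 11.5.4).
- **Capture.** Protocol 6.5.2 provides AECOPD-driven contacts "for each AECOPD occurring from first vaccination up to study conclusion".
- **Entry.** Protocol 5.2 requires a documented history "of at least 1 moderate or severe AECOPD within the 12 months before Screening".

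No analysis that keeps the excluded subjects is planned as a companion to this one.

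**The concern.** The rule selects subjects on something that happens after vaccination. The exclusion sentence gives no lower time limit, but every subject had an AECOPD in the year before Screening, so an open-ended reading would remove everyone. The only workable reading is from Dose 1, where capture begins, to 1 month post-Dose 2.

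Two things are at stake. First, subjects and events are lost from a small study. Second, if some patients exacerbate more readily than others, those still event-free at about Day 90 are on average the less prone ones. The reported times would then look better than they are for the cohort as a whole, in both groups, even if the vaccine did nothing. They would also appear beside incidence rates that start on the same date but describe a different set of people, and nothing in the plan tells the reader so.

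**Working it through.** **The plan's own figure.** The only sample-size statement (Protocol 11.4) concerns adverse events: 1 - 0.99^70 = 50.5% and 1 - 0.95^70 = 97.2%, which agree with its claims of more than 50% and more than 97%. There is no figure for AECOPD, so the rates below are assumptions.

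**Window.** Dose 1 is Day 0, Dose 2 is Day 60, and 1 month post-Dose 2 is Day 90. The intervals in Protocol Table 9 allow 60-75 plus 30-45 days, so 90-120 days. I use t0 = 90/365 = 0.2466 years, the short end.

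**Model.** AECOPD counts are negative binomial, as in SAP 6.1.3, with mean μ per year and dispersion k. Each group has 70 subjects, with no vaccine effect and no dropout.

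- Excluded: 1 - (1 + kμt0)^(-1/k)
- Mean rate in those kept: μ / (1 + kμt0)
- 1-year AECOPD-free share, everyone: (1 + kμ)^(-1/k)
- The same, those kept: [(1 + kμ(1 + t0)) / (1 + kμt0)]^(-1/k)
- First events per group: number analysed × (1 - AECOPD-free share)

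**Worked case, μ = 1.5, k = 0.7.** 1 + 0.7 × 1.5 × 0.2466 = 1.259. Excluded: 1 - 1.259^(-1/0.7) = 28.0%, leaving 50.4 of 70. Rate in those kept: 1.5/1.259 = 1.19. AECOPD-free share: 2.05^(-1/0.7) = 35.9% for everyone, and (2.309/1.259)^(-1/0.7) = 42.0% for those kept. First events: 70 × 0.641 = 44.9 against 50.4 × 0.580 = 29.2, a loss of 35%.

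| μ | k | Excluded | Rate in those kept | AECOPD-free at 1 year, everyone → kept | First events lost |
|---|---|---|---|---|---|
| 1.0 | 0.3 | 21% | 0.93 | 41.7% → 44.0% | 24% |
| 1.0 | 0.7 | 20% | 0.85 | 46.9% → 51.2% | 27% |
| 1.0 | 1.0 | 20% | 0.80 | 50.0% → 55.5% | 29% |
| 1.5 | 0.3 | 30% | 1.35 | 29.0% → 32.2% | 33% |
| 1.5 | 0.7 | 28% | 1.19 | 35.9% → 42.0% | 35% |
| 1.5 | 1.0 | 27% | 1.10 | 40.0% → 47.7% | 36% |
| 2.5 | 0.3 | 43% | 2.11 | 15.5% → 19.5% | 46% |
| 2.5 | 0.7 | 40% | 1.75 | 23.6% → 32.0% | 47% |
| 2.5 | 1.0 | 38% | 1.55 | 28.6% → 39.3% | 47% |

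**No heterogeneity.** With identical risk the excluded share is 1 - exp(-μt0) = 22%, 31% or 46%. The rate in those kept equals the rate in everyone, so the level is unbiased and only data are lost.

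**Longer window.** At μ = 1.5 and k = 0.5, 120 days instead of 90 raises the excluded share from 28.8% to 35.6%.

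**Group contrast.** Without an early vaccine effect both groups are selected alike and the expected hazard ratio stays 1.00. At k = 0.7 and μ = 1.0/1.5/2.5, an early-only 50% increase gives 0.94/0.93/0.90, and an early-only 30% reduction gives 1.04/1.05/1.07. At μ = 1.5 the sampling uncertainty with the rule is exp(±1.96 × √(2/29.2)) = 0.60-1.67. If instead a true rate ratio of 0.70 holds from Dose 1 onward (μ = 1.5, k = 0.5), 28.8% of controls and 21.6% of vaccinees are removed. The ratio in those kept at Day 90 is then [1.05/(1 + 0.5 × 1.05 × 0.2466)] / [1.5/(1 + 0.5 × 1.5 × 0.2466)] = 0.930/1.266 = 0.73.

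**The case against.** The case for leaving the text alone is a fair one.

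- **It is open and minor.** The rule is stated identically in the protocol and SAP. The endpoint is tertiary, and Protocol 11.13 calls group comparisons descriptive and asks for caution. At k = 0.7 the shift in the AECOPD-free share (4, 6 or 8 points) is smaller than the 95% half-width among those kept (13, 14 or 14 points). This stands, and it limits the weight of the point.
- **The lower-risk subset is not a documented fact.** It needs between-subject heterogeneity, and the documents give no dispersion. This stands too. But the SAP's negative binomial model presumes such heterogeneity, and the loss of data does not depend on it.
- **The plan names no curve or AECOPD-free share.** True. The share is used here only as a scale for the shift.
- **The comparison population is already reduced.** A moderate or severe AECOPD that is ongoing or recently resolved defers vaccination (Protocol 7.5), and a late or missed Dose 2 removes the subject from the ATP efficacy cohort. This narrows the gap by an unknown amount. It does not close it: mild episodes, episodes resolved in time and episodes after Dose 2 need not affect the schedule.
- **First AECOPD among those event-free since vaccination is a coherent quantity.** So it is, but it is not the endpoint defined for all subjects.

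A reader might infer more: that the rule biases vaccine efficacy or manufactures a group difference. The documents do not support that. Vaccine efficacy comes from the incidence model, which has no such exclusion, and without an early vaccine effect the selection is balanced in expectation. A reader might also add the sputum-based exclusion in SAP 7.1.3, or the missing time origin and group term in the paragraph headed "Time to first AECOPD event by baseline status - Cox regression model". Both are worth clarifying, but they concern other analyses and are no evidence for this point.

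**Conclusion.** The point holds in limited form. The exclusion selects on a post-vaccination outcome, departs from the endpoint as defined, and gives a different population from the incidence analysis with the same start date. Under the assumed 1.0-2.5 AECOPD per year, dispersion 0.3-1.0 and a 90-day window, it costs about 20-43% of subjects and 24-47% of usable first events. It raises the 1-year AECOPD-free share by about 2-11 points if risk varies between subjects, and by nothing if it does not. Overlap with ATP exclusions would make the mismatch with the ATP incidence analysis somewhat smaller. Any effect on the group contrast requires an early vaccine effect and is small beside the sampling error. The harm is to the interpretation and precision of one tertiary, descriptive result. Incidence rates, vaccine efficacy and iSRC review are untouched. The change is worth making because it costs little and the selection serves no purpose that a labelled sensitivity analysis would not serve.

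**What to change.** In SAP 6.1.4 and Protocol 11.10:

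1. Include all cohort subjects still followed at 1 month post-Dose 2, whatever happened earlier, and analyse time from that date to the first AECOPD with onset after it.
2. Let a subject with an AECOPD ongoing at that date enter the risk set when it ends. At an assumed 14-day duration this concerns about μ × 14/365 = 4-10% of subjects for μ = 1.0-2.5.
3. Label the result *first AECOPD after 1 month post-Dose 2*, and report by group how many subjects had an earlier AECOPD.
4. Keep the present exclusion as a sensitivity analysis.

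The drawback is that for early exacerbators the counted event is not their first since Dose 1. Under the assumptions above they supply 24-47% of counted events, which is why the label and the count in item 3 are needed.

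The cost is a few lines of text and a little programming. No new data are required, because onset and end dates of confirmed AECOPD are recorded from Visit 1 (Protocol 4.1.1).

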6.1.5. Analysis of HRQOL, lung capacity and exercise capacity

The analysis will be performed on the TVC. If the percentage of vaccinated subjects excluded from the ATP cohort for efficacy is at least 10%, a second analysis will be performed on the ATP cohort for efficacy to complement the first analysis.

Descriptive statistics (median, mean, range, standard deviation, first and third quartiles) on the **EXACT-PRO**, **CAT**, **SGRQ-C** and **mMRC** scores, on **FEV₁% of predicted normal value** and on the **6MWT** scores will be tabulated by specified visit.

Descriptive summaries **rescue medication and healthcare use for AECOPD** will be provided.

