All factors will have equal weight in the minimisation algorithm.

Subjects will be randomised using a centralised randomisation system on internet (SBIR) at first dose. Treatment number allocation (without randomisation) will also occur at Dose 2 using SBIR.

- **Blinding:** observer-blind

Table 5 Blinding of study epoch

Study Epochs	Blinding
Epoch 001	observer-blind

- **Sampling schedule.**
 - **Blood samples for safety assessment** * (haematology/ biochemistry parameters) will be collected from all subjects at the Screening Visit (pre-Day 0), Visit 1 (Day 0), Visit 2 (Day 7), Visit 3 (Day 30), Visit 4 (Day 60), Visit 5 (Day 67), Visit 6 (Day 90), Visit 8 (Day 270) and at Visit 10 (Day 450).

* Additional blood sample(s) for safety assessment may be taken at the discretion of the investigator if deemed necessary.
 - **Blood samples for assessment of humoral immunogenicity** will be collected from all subjects at Visit 1 (Day 0), Visit 3 (Day 30), Visit 4 (Day 60), Visit 6 (Day 90), Visit 8 (Day 270) and at Visit 10 (Day 450).

- **Blood samples for assessment of cell-mediated immunogenicity (CMI)** will be collected from all subjects in the CMI sub-cohort at Visit 1 (Day 0), Visit 6 (Day 90), Visit 8 (Day 270) and at Visit 10 (Day 450).
- **Blood samples for biomarkers** will be collected from all subjects at Visit 1 (Day 0), Visit 10 (Day 450) and at each AECOPD visit from first vaccination to study conclusion.
- **Blood samples for assessment of haematology** parameters will be collected at each AECOPD visit.
- **Sputum samples** will be collected from all subjects at the Screening Visit (pre-Day 0), Visit 6 (Day 90), Visit 7 (Day 180), Visit 8 (Day 270), Visit 9 (Day 360), Visit 10 (Day 450) and at each AECOPD visit from first vaccination to study conclusion.
- **COPD symptoms:** All subjects will be asked to record COPD symptoms in their electronic Diary Card:
 - Daily in the morning throughout the study (including during AECOPD): **morning symptoms**.
 - Daily at bedtime throughout the study (including during AECOPD): **EXACT-PRO**.
- **HRQOL assessments:**
 - All subjects will be asked to complete the **COPD assessment test (CAT)** at the Screening Visit (pre-Day 0), Visit 8 (Day 270), Visit 10 (Day 450) and at each AECOPD visit from first vaccination to study conclusion.

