2. STUDY DESIGN

Figure 1 Study design overview

[figure not shown]
$N \geq 70/\text{group}$

40 – 80 years

10-30 years
COPD patients

10 μ g Ag/ AS01 E

108

Scr = Screening; **V** = Visit; **D** = Day; **rando** = randomisation; **VACC** = vaccination; **BS(1)** = blood sample for safety; **BS(2)** = blood sample for humoral immunogenicity; **BS(3)** = blood sample for cell-mediated immunity (CMI); **BS(4)** = blood sample for biomarkers; **SP** = sputum sample

In addition to the scheduled study visits depicted above, **ad hoc AECOPD-driven study visit(s) and/or phone contact(s)** will take place for each AECOPD occurring from first vaccination up to study conclusion. An AECOPD visit will be scheduled as soon as possible after the onset of AECOPD symptoms (maximum 96 hours after and, if applicable, preferably before starting treatment with antibiotics). In addition, follow-up phone call(s) and/or visit(s) will take place to determine the end of the AECOPD. These contacts will take place at least every 2 weeks, until the AECOPD has resolved.

Experimental design: Phase II randomised, observer-blind, placebo-controlled, multi-centre study with 2 parallel groups.

Duration of the study: for each subject enrolled, the study will last approximately 16 months from Visit 1 up to study end

The following group names will be used for the statistical analyses:

Group order in tables	Group label in tables	Group definition for footnote
1	10-AS01E	2 doses of AS01e adjuvanted vaccine containing 10 mcg of each antigen
2	Control	2 doses of saline solution

Statistical Analysis Plan

Study alias & e-track number(s): NTHi-004 (200157)

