4.3. Tertiary endpoints

- Number of cases of NTHi-associated moderate and severe AECOPD, over a period starting 1 month post-Dose 2 and lasting for 1 year, in all subjects.
- Number of cases of NTHi-associated AECOPD (any severity), over a period starting 1 month post-Dose 2 and lasting for 1 year, in all subjects.
- Number of cases of moderate and severe AECOPD (any cause), over a period starting 1 month post-Dose 2 and lasting for 1 year, in all subjects.
- Number of cases of AECOPD (any cause, any severity), over a period starting 1 month post-Dose 2 and lasting for 1 year, in all subjects.
- Time to first AECOPD, in all subjects.
- Assessment of EXACT-PRO score, daily at bedtime throughout the study, in all subjects.
- NTHi presence in sputum, at Screening, Day 90, Day 180, Day 270, Day 360 and Day 450, and from first vaccination to study conclusion for each AECOPD, in all subjects.
- Assessment of CAT score, at Screening, Day 270 and Day 450, and from first vaccination to study conclusion for each AECOPD, in all subjects.
- Assessment of SGRQ-C score, at Screening, Day 270 and Day 450, in all subjects.
- Assessment of mMRC scale, at Screening, Day 270 and Day 450, and from first vaccination to study conclusion for each AECOPD, in all subjects.
- Occurrence of rescue medication use, over a period starting 1 month post-Dose 2 and lasting for 1 year, in all subjects.
- Occurrence of healthcare use for AECOPD, over a period starting 1 month post-Dose 2 and lasting for 1 year, in all subjects.

Statistical Analysis Plan

Study alias & e-track number(s): NTHi-004 (200157)

- Assessment of FEV1% of predicted normal value at Screening, Day 270 and Day 450, in all subjects.
- Assessment of 6MWT score, at Screening and Day 450, in all subjects.
- Occurrence of selected biomarkers in a subset of blood samples, at Day 0 and Day 450, and from first vaccination to study conclusion for each AECOPD, in all subjects.
- Presence of respiratory viral pathogens in sputum (including respiratory syncytial virus, parainfluenza virus, enterovirus/ rhinovirus, metapneumovirus, influenza virus, adenovirus, bocavirus and coronavirus) at Screening, Day 90, Day 180, Day 270, Visit Day 360 and Day 450 and at each AECOPD visit from first vaccination to study conclusion, in all subjects.

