7.1.6. EXACT-PRO derived AECOPD definitions and calculation rules

Start of an EXACT-PRO signal for exacerbation (as in EXACT-PRO user Manual and in Makay, et al., 2014):

1. *An EXACT-PRO exacerbation is defined as a 12 point increase above baseline for 2 consecutive days, or a nine point increase for 3 consecutive days.*
2. *The baseline score corresponds to the average EXACT score during a baseline period defined as days 14 to 8 preceding exacerbation onset*
3. *Exacerbation onset will be taken as the first day in which at least two symptoms (at least 1 major) are present and have not been discounted (see above).*
4. *Only symptom data collected during the study period will be used to define the start of an exacerbation.*

End/recovering of an EXACT-PRO signal of an exacerbation:

1. *The end/recovering of an EXACT-PRO signal of an exacerbation corresponds to the day at the EXACT-PRO score return to its baseline value.*
2. *The length of a signal of an exacerbation will be at least of 2 days. So rule 1 will only apply from the third day onwards.*

Missing data:

Days with missing data will not be ignored when defining start of a signal: e.g., if a patient has two qualifying symptoms followed by a missing day, if the next day with data has two qualifying symptoms this will not be defined as an exacerbation.

Statistical Analysis Plan

Study alias & e-track number(s): NTHi-004 (200157)

7.1.7. “e-diary derived AECOPD” definitions and calculation rules

The definition of an AECOPD case definition from section 5.3.1.2 of the Protocol is what we will call here an “e-diary derived (AECOPD) signal”. In this paragraph, only the derivation of occurrence and length of e-diary signals is described. Derivation of occurrence and length of AECOPDs is described in Section 7.1.11.

Start of an e-diary signal for exacerbation:

1. An exacerbation is defined as a worsening of at least 2 symptoms for ≥ 2 consecutive days where at least one of the symptoms is major.
2. The same two symptoms do not have to be present on both days as long as at least one major symptom is present on both days.
3. Any symptom that has occurred consecutively for 5 days or more prior to a potential exacerbation should be discounted from the symptoms that define an exacerbation.
4. Exacerbation onset will be taken as the first day in which at least two symptoms (at least 1 major) are present and have not been discounted (see above).

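### The level of the daily EXACT-PRO score is summarised only by visit, with no rule linking diary days to visits and no summary over follow-up

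*SAP*

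**What the plan says.** **How the score is collected.** Protocol section 3 places EXACT-PRO under COPD symptoms, separately from the HRQOL assessments, with the schedule "Daily at bedtime throughout the study (including during AECOPD"). SAP section 4.3 makes it a tertiary endpoint: "Assessment of EXACT-PRO score, daily at bedtime throughout the study, in all subjects". The visit procedures in protocol Tables 7 and 8 do not list it. Protocol section 6.6.25 names the clinic questionnaires as CAT, SGRQ-C and mMRC only.

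**How its level is summarised.** SAP 6.1.5 covers EXACT-PRO, CAT, SGRQ-C, mMRC, FEV1% predicted and 6MWT in a single sentence: descriptive statistics on these "scores will be tabulated by specified visit". Protocol 11.11 does the same. For EXACT-PRO there is no list of visits, no choice of day, no averaging window and no completeness rule, and the sentence does not mention group.

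**Where the daily series is used.** SAP 7.1.6 derives episodes from consecutive days: "An EXACT-PRO exacerbation is defined as a 12 point increase above baseline for 2 consecutive days", or nine points for three days, against a mean over days 14 to 8 before onset. SAP 6.1.4 tabulates "evening e-diary alerts (EXACT-PRO") with and without site visits. It also compares exacerbation periods "as defined clinically or via the morning diary cards or the evening diary cards will be tabulated and presented graphically".

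**Visit spacing.** Protocol Table 9, footnote 5, keeps scheduled visits out of the 7 days around an AECOPD visit. Protocol 6.5.3 lets an end-of-AECOPD contact be combined with a scheduled visit.

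**The concern.** A diary completed every evening for about 15 months measures symptom burden over time. A visit table suits a questionnaire completed at the visit. For a diary it leaves the programmer to choose which evenings represent a visit, and different choices give materially different tables from the same data.

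The content of the result is also at stake. If the vaccine reduces exacerbations, part of any benefit in symptoms should appear on exacerbation days. The diary was kept on those days, but a table built on scheduled-visit scores would tend to miss them. As written, no planned output answers whether vaccinated subjects had a lower average daily symptom score over the follow-up year.

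**Working it through.** The documents give no figure for the share of diary entries used. The stated study length can be checked first, because it sets the denominator.

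**Length of the daily series**
- The SAP (section 2) states: "for each subject enrolled, the study will last approximately 16 months from Visit 1 up to study end". The last scheduled visit is "Visit 10 (Day 450") (protocol section 3).
- Nominal schedule: 450 / 30.4375 = 14.8 months.
- Latest allowed windows in Table 9: 75 + 45 + 390 = 510 days, and 510 / 30.4375 = 16.8 months.
- The stated length lies between the two. Nominal entries from Day 0 to Day 450: 451.

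**Share of entries in the 6.1.5 score table** = scores used / possible entries

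| Reading of 6.1.5 (each an assumption) | Calculation | Share |
|---|---|---|
| One score per visit, Visits 1 to 10 | 10/451 | 2.2% |
| Same, latest windows | 10/511 | 2.0% |
| Screening and a 14- to 28-day run-in added | 11/465 to 11/479 | 2.4% to 2.3% |
| HRQOL visits only (Screening, Day 270, Day 450) | 3/465 to 3/479 | 0.6% |
| 7-day mean at each of Visits 1 to 10 | 70/451 | 15.5% |

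The width of this range follows from the missing rule.

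**Days removed by the spacing rule.** With r AECOPD visits a year (assumed 1 to 3), the 7 days after each take up r × 7 / 365.25 of the year: 1.9%, 3.8% and 5.7% for r = 1, 2 and 3. This is a small share of days, but it falls close to exacerbation onset.

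**Precision of a period mean.** Let ρ be the share of one-day variance that lies between subjects (assumed 0.5 to 0.8), with equal correlation between all days of a subject. The variance of a k-day mean relative to one day is ρ + (1 − ρ)/k.
- k = 28: 0.5 + 0.5/28 = 0.52, and 0.8 + 0.2/28 = 0.81. A 28-day mean has 48% to 19% less variance than a single day.
- k = 7: 0.5 + 0.5/7 = 0.571, and 0.8 + 0.2/7 = 0.829. If the table already used 7-day means, going to 28 days would gain only 1 − 0.518/0.571 = 9%, or 1 − 0.807/0.829 = 3%.
- If neighbouring days are more alike than distant ones, the gain at the same ρ is smaller.

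**What the other EXACT-PRO outputs cover.** Section 7.1.6 defines when an episode starts and ends. Section 6.1.4 counts alerts and compares periods between detection methods, and it specifies results by group only for time to first AECOPD. Neither section describes the level of the score.

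**The case against.** Several points weigh against a strong reading.

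- **Use of the data.** A reader might infer that the trial uses only about 2% of its EXACT-PRO data. The documents do not support this. Deriving episodes, alerts and concordance requires, in principle, every available daily entry, and these outputs target exacerbation days. The 2% applies to the score table alone, and only under one reading.
- **Avoidance of exacerbation days.** A reader might also infer that days near an AECOPD visit are excluded by design. That goes too far. Footnote 5 governs scheduled visits, whereas 6.1.5 speaks of specified visits. CAT and mMRC, in the same sentence, are also assessed at AECOPD visits, so those visits may be included. An AECOPD may still be unresolved after 7 days, and an end-of-AECOPD contact may coincide with a scheduled visit. What stands is that scheduled-visit scores lean towards stable days.
- **The table shells.** The SAP refers to a separate TFL annex, which was not available. It may name visits or windows.
- **Dilution.** If benefit falls mainly on exacerbation days, a mean over mostly stable days dilutes it. This is fair: a period mean measures overall burden. It does at least count exacerbation days in proportion to their number. Exacerbation frequency is analysed directly in SAP 6.1.3.
- **Weight.** This is one of 16 tertiary endpoints, and all comparisons are descriptive. That limits the consequence, but the endpoint still lacks a usable summary.

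**Conclusion.** The point holds for the level of the EXACT-PRO score. A daily endpoint is summarised only by visit, without a mapping from days to visits and without any summary over follow-up. The analyses that do use the daily series do not describe score level by group.

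On one score per scheduled visit, the table rests on about 2% of entries (0.6% to 15.5% across the readings considered) and leans towards stable days. The 19% to 48% reduction in variance from a 28-day mean depends on single-day scores, an assumed ρ of 0.5 to 0.8 and equal correlation between days. No figure in the documents supports these assumptions, so this is an illustration of the possible gain.

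This is more than missing detail, because a by-group mean over fixed periods is a concrete alternative that uses data already collected. The effect is on the interpretability of one tertiary, descriptive endpoint. The primary objective and the sample size are not affected.

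**What to change.** In SAP 6.1.5, replace or supplement the by-visit EXACT-PRO table with:

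- descriptive statistics by group of each subject's mean daily score per 4-week period, and over the 1-year period from 1 month post-Dose 2, with AECOPD days included;
- a stated minimum share of completed diary days for a period to count;
- the mean over the Screening-to-Visit 1 run-in (14 to 28 days, Table 9) shown as baseline, with change from baseline or adjustment for it as an exploratory addition.

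If the by-visit table is kept, name the visits and the day or averaging window used.

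Four-week intervals match those the SAP already uses for yearly exacerbation rates (section 7.1.3). The nominal span from Day 90 to Day 450 is 360 = 12 × 28 + 24 days, so the rule should say how a short last period is handled.

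The cost is SAP wording, one derived dataset and a few extra tables, with no new data collection. The gain in precision is uncertain, because the within-subject correlation is unknown, and it is smaller under serial correlation.
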